**Table 5-2 Rules for flagging variables (values)**

Timing of measurement	Type of data	Rule
Baseline	All data	
The last non-missing measurement made prior to or on the date of administration of the first dose of study treatment (the reference start date / Day 1). If a patient did not receive any dose of study treatment then the randomization date will be used. Only date part is considered if just one assessment on Day 1.
 
If there are multiple assessments on Day 1, following rules will apply:
 
 
(a) If assessment time exists, 
 
- select the last available measurement prior to reference start date/time considering time;
 
- if no measurement prior to reference start date/time considering time, select the earliest measurement post reference start date/time considering time .
 
 
 
(b) If assessment time does not exist, select the available measurement from the lowest CRF visit number.
 

Post-baseline efficacy	All data	
 
• The measurement closest to the target will be used. In the event two measurements are taken equally apart (e.g. 1 before target date and 1 after) the first one will be used.
 
• Cases where the same parameter is recorded more than once on the same date will be handled as follows: 
 
◦ If time of completion exists the earliest measurement will be used;
 
◦ If time does not exist the measurement from the lowest CRF visit number will be used.
 
 
 

Post-baseline safety	Summary visit information [REDACTED]	
 
• The measurement closest to the target will be used. In the event two measurements are taken equally apart (e.g. 1 before target date and 1 after) the first one will be used.
 
• Cases where the same parameter is recorded more than once on the same date will be handled as follows: 
 
◦ If time of completion exists the earliest measurement will be used;
 
◦ If time does not exist the measurement from the lowest CRF visit number will be used.
 
 
 

Timing of measurement	Type of data	Rule
Post-baseline safety	Notable abnormalities (e.g. lab)	The most extreme measurement in the window will be used. Note this means a patient can have a notably high and notably low measurement within a window.

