8.5 Adjudication Committee

Not required.

9 Data analysis

The analyses will be conducted on all patient data at the time the trial ends and at the time when any interim analyses are performed. Any data analysis carried out independently by the investigator should be submitted to Novartis before publication or presentation.

Summary statistics for continuous variables will include N, mean, standard deviation, minimum, lower quartile, median, upper quartile, maximum. Summary statistics for discrete variables will be presented in the number and percent of patients in each category.

If not otherwise specified, p-values will be presented as two-sided p-values and two-sided confidence intervals will be displayed.

The default level of significance will be set to 5% (two-sided, family-wise type-I-error).

The baseline value is defined as the last assessment prior to first dose administration. In case the scheduled baseline assessment value is missing the screening value will be used instead.

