9.4.3 Handling of missing values/censoring/discontinuations

For time points with missing data in one of the domains of the ESSDAI the total ESSDAI score will be set to missing. Alternative approaches of imputing these missing values might be considered.

Patients with missing data at one or more post-dose time points post baseline will be included in the analysis. If the baseline ESSDAI value is missing (and there is no the screening value available to replace it) the patient will be excluded from the primary analysis of change from baseline in ESSDAI.

The planned primary repeated measures mixed effects model assumes that missing values are missing at random. The reasonableness of this assumption will be checked during the blinded review of the data and if necessary further methods may be applied.

Sensitivity analyses of imputing might be considered to test the robustness of the results to the missing data assumptions. The following approaches could be explored:

- impute data based on the placebo treatment group data;
- impute data based on patients' data who discontinued treatment but continued study visits in case a sufficiently high number of such cases is observed.

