### Baseline

The baseline value is defined as the last assessment prior to first dose administration. In case the scheduled baseline assessment value is missing, the screening value will be used instead.

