### 2.6.3 Handling of missing values/censoring/discontinuations

For the secondary analyses, missing data will not be imputed. If missing data occurs in a domain the corresponding total measurement will be set to missing. If a baseline assessment is missing (and there is no the screening value available to replace it) the corresponding change from baseline value will be missing.

[REDACTED]

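### SAP Table 5-2 can take a Day 1 value measured after the first dose as baseline, contradicting the pre-dose definition in SAP 2.1.1 and protocol section 9

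*SAP*

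**What the plan says.** Two places give the definition. SAP 2.1.1 states: "The baseline value is defined as the last assessment prior to first dose administration". It adds: "In case the scheduled baseline assessment value is missing, the screening value will be used instead". Protocol section 9 has the same definition and the same fallback: "In case the scheduled baseline assessment value is missing the screening value will be used instead".

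Two more places say what follows if no such value exists. For the primary variable, protocol 9.4.3 says: "If the baseline ESSDAI value is missing (and there is no the screening value available to replace it) the patient will be excluded". For secondary variables, SAP 2.6.3 says: "If a baseline assessment is missing (and there is no the screening value available to replace it) the corresponding change from baseline value" is set to missing.

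SAP Table 5-2, in its baseline row for all data, words the rule differently. It starts from the calendar date: "The last non-missing measurement made prior to or on the date of administration of the first dose of study treatment". Then it says: "Only date part is considered if just one assessment on Day 1". For several Day 1 assessments with recorded times, it first looks for the last one before the dose. Failing that: "if no measurement prior to reference start date/time considering time, select the earliest measurement post reference start date/time considering time". Several untimed values are resolved by the lowest CRF visit number.

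SAP section 4, on changes from the protocol's analyses, lists none.

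**The concern.** The definition and the derivation table give different baselines for the same patient, and the table is the more operational of the two. The clause for several timed values cannot be explained as an assumption that anything dated Day 1 precedes dosing, because it uses times known to be after the dose.

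The situation can arise. Among the Day 1 samples and assessments in protocol Table 6-1, only the PK sample is labelled pre-dose. Patients stay at the site for at least 6 hours after the first dose (protocol 3.6 and 5.5.4). SAP 5.1 maps repeat and unscheduled measurements in the same way as scheduled ones. A footnote to Table 6-1 allows the first dose one calendar day after randomization, so a valid baseline-visit value can be dated the day before Day 1.

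At stake is every quantity measured against baseline. The laboratory shift tables compare the worst post-baseline value with baseline (SAP 2.7.3). A notable blood pressure is a change of at least 25% from baseline (SAP 5.3). For efficacy variables, baseline is subtracted to form the outcome and is also a model covariate (SAP 5.4.1.1 for ESSDAI).

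**Working it through.** The plan states no figure on this point, so there is none to reproduce. I wrote out both rules and applied them to seven constructed patterns of assessments. The word prior in the clause for several Day 1 values can be read in two ways: earlier on Day 1 only, or at any earlier time including screening. Both are shown.

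| Pattern | SAP 2.1.1 and protocol 9 | Table 5-2, prior = Day 1 only | Table 5-2, prior = any earlier value |
|---|---|---|---|
| 1. Screening; one pre-dose Day 1 value | Pre-dose Day 1 | Pre-dose Day 1 | Pre-dose Day 1 |
| 2. Screening; one pre-dose and one post-dose Day 1 value | Pre-dose Day 1 | Pre-dose Day 1 | Pre-dose Day 1 |
| 3. Screening; one post-dose Day 1 value | Screening | Post-dose | Post-dose |
| 4. Screening; two timed post-dose Day 1 values | Screening | First post-dose | Screening |
| 5. No screening; two timed post-dose Day 1 values | Missing | First post-dose | First post-dose |
| 6. Screening; baseline visit the day before dosing; one post-dose Day 1 value | Baseline visit | Post-dose | Post-dose |
| 7. No screening; one post-dose Day 1 value | Missing | Post-dose | Post-dose |

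The rules conflict in four of the seven patterns (3, 5, 6 and 7) under either reading, and in a fifth (4) under the Day 1 reading. These counts describe the rules; they do not say how often each pattern will occur.

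Three things follow.

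- The date-only sentence is the main proof. In patterns 3 and 6 it puts a post-dose value ahead of an available pre-dose value, however prior is read.
- The clause for several Day 1 values always gives a post-dose baseline when there is no earlier value (pattern 5), where protocol 9.4.3 and SAP 2.6.3 give exclusion or a missing change. It displaces screening only under the Day 1 reading (pattern 4).
- Under the wider reading the table is inconsistent with itself: one post-dose value displaces screening (pattern 3), but two do not (pattern 4).

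On size, suppose k patients in an arm of about 45 have baseline shifted by d. The unadjusted mean change then moves by k × d / 45. In a model with baseline as a covariate it moves by roughly b × k × d / 45, where b is the slope of the Week 24 value on baseline. A difference from placebo moves only by the imbalance between arms. The documents give none of k, d or b, so no number follows. If every Day 1 assessment is pre-dose, k = 0 and so is the effect.

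**The case against.** The best counter-argument is that the plan's workflow protects the endpoints that matter most. Baseline ESSDAI must be entered into the IRT for stratification (protocol 6.2.4). ESSPRI of at least 5 at baseline is inclusion criterion 5, and the site contacts the IRT only after confirming eligibility (protocol 5.3). A patient handled per protocol therefore has both scores before randomization, and so before dosing. This stands. It makes an effect on the primary analysis unlikely. It does not cover laboratory values, vital signs or repeat readings.

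A second argument is that the clause for several Day 1 values, read literally, acts only when no earlier value of any kind exists. That reading is open. A reader might infer from the clause alone that screening is always ignored; the text does not settle this. The date-only sentence needs no such reading.

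A reader might also infer that the methylprednisolone pre-medication biases the treatment comparison through a post-dose baseline. The documents do not support that. Every arm receives it, about 1 hour before the dose (protocol 5.1.2), so it is not arm-specific. A value taken between steroid and study drug meets the SAP 2.1.1 definition in any case.

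Finally, correcting the rule has a cost. FACIT-F, SF-36 and PaGA have no screening assessment in Table 6-1, and protocol 6.4.3.2 starts FACIT-F at baseline. Discarding a post-dose Day 1 value there leaves nothing to replace it. This stands as a cost, but SAP 2.6.3 already prescribes that outcome.

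**Conclusion.** The contradiction is real and undeclared: Table 5-2 can select a post-dose baseline that SAP 2.1.1 and protocol section 9 do not allow. It bites in narrow circumstances. With a timed pre-dose value on Day 1 the two rules agree (patterns 1 and 2). They part when the only Day 1 value, or every timed one, follows the dose.

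The practical exposure is mainly laboratory, vital-sign and other repeat or unscheduled Day 1 values. A reader might go further and infer a measurable bias in the ESSDAI result. That would need some number of patients whose ESSDAI baseline was taken after dosing and a shift in score within hours. The documents give neither, and the randomization workflow points the other way. The number of affected patients is unknown and may be zero. The case for correction rests on having one unambiguous baseline rule, not on a demonstrated effect.

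**What to change.** Reword the baseline row of Table 5-2 as follows.

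- When the assessment time and the first-dose time are both recorded, take the last non-missing value before the first-dose date and time. Baseline-visit and screening values count.
- If there is no such value, set baseline to missing, with the consequences already stated in protocol 9.4.3 and SAP 2.6.3. State that the same holds for safety variables, which those two sections do not cover.
- Use the date alone only when the time is missing. The existing lowest-visit-number rule can stay for several untimed Day 1 values.
- Delete the post-dose fallback.

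If the sponsor prefers to keep the present rule, it should be declared and justified in SAP section 4, with a count of patients whose baseline is timed after the dose.

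The work is one table cell and its program. There are two analytical costs. A patient whose only Day 1 FACIT-F, SF-36 or PaGA value is post-dose loses the change from baseline for that endpoint. Where screening is used instead, it may be up to four weeks old. Nothing is lost from the post-baseline visits, because the first post-baseline window in SAP 5.1 opens on Day 2.

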## 5.2 Imputation rules

### 5.2.1 Study drug

No imputation will be made to the start date and end date of study treatment.

### 5.2.2 AE date imputation

The following missing dates will not be imputed:

- Missing AE start dates
- AE start dates missing the year
- Partial/missing AE end dates

For other type of partial missing start dates, rules specified in the following tables will be used.

	Day	Month	Year
Partial Adverse Event Start Date	Not used	MON	YYYY
Treatment Start Date	Not used	TRTM	TRTY

The following matrix explains the logic behind the imputation.

	MON MISSING	MON < TRTM	MON = TRTM	MON > TRTM
YYYY MISSING	( 1 ) No convention			
YYYY < TRTY	( 2.a ) Before Treatment Start	( 2.b ) Before Treatment Start	( 2.b ) Before Treatment Start	( 2.b ) Before Treatment Start
YYYY = TRTY	( 4.a ) Uncertain	( 4.b ) Before Treatment Start	( 4.c ) Uncertain	( 4.c ) After Treatment Start
YYYY > TRTY	( 3.a ) After Treatment Start	( 3.b ) After Treatment Start	( 3.b ) After Treatment Start	( 3.b ) After Treatment Start

Impute AE start date -

1. If the AE start date year value is missing, the date uncertainty is too high to impute a rational date. Therefore, if the AE year value is missing, the imputed AE start date is set to NULL.
2. If the AE start date year value is less than the treatment start date year value, the AE started before treatment. Therefore:
  - a. If AE month is missing, the imputed AE start date is set to the mid-year point (01JulYYYY).

- b. Else if AE month is not missing, the imputed AE start date is set to the mid-month point (15MONYYYY).
3. If the AE start date year value is greater than the treatment start date year value, the AE started after treatment. Therefore:
  - a. If the AE month is missing, the imputed AE start date is set to the year start point (01JanYYYY).
  - b. Else if the AE month is not missing, the imputed AE start date is set to the later of (month start point (01MONYYYY), treatment start date + 1 day).
4. If the AE start date year value is equal to the treatment start date year value:
  - a. And the AE month is missing the imputed AE start date is set to the treatment start date + 1 day.
  - b. Else if the AE month is less than the treatment start month, the imputed AE start date is set to the mid-month point (15MONYYYY).
  - c. Else if the AE month is equal to the treatment start date month or greater than the treatment start date month, the imputed AE start date is set to the later of (month start point (01MONYYYY), treatment start date + 1 day).

If AE end date is available and the imputed AE start date is greater than the AE end date, then imputed AE start date should be set to the AE end date.

### 5.3 Parameters derivations

### **Notable vital signs abnormalities in adult patients (≥18 years of age)**

Post-baseline vital signs will be flagged as notable abnormalities as follows:

1. Systolic/Diastolic blood pressure:  $\geq 25\%$  decrease or  $\geq 25\%$  increase from baseline
2. Pulse:  $\geq 110$  bpm with  $\geq 15\%$  change from baseline, or  $< 50$  bpm with  $\geq 15\%$  change from baseline

## 5.4 Statistical models

### 5.4.1 Primary analysis

The primary endpoint will be analyzed using a 3-step approach. An overview of the approach is shown in [Section 2.5.2](#). In the following sections, some details on MMRM and DR model families are provided, followed by the MCPMod methodology.

#### 5.4.1.1 Repeated measures analysis

As a first step in the dose-response characterization a repeated measures model will be fitted to the changes from baseline in ESSDAI up to week 24. The change from baseline in ESSDAI is assumed to be normally distributed.

An MMRM model will be fitted to the changes from baseline in ESSDAI including all time points until week 24 including the following fixed factors

- treatment group
- (analysis) visit
- treatment group by visit interaction
- stratification factor baseline ESSDAI score  $<10$  or  $\geq 10$
- geographic region

as well as baseline ESSDAI as a continuous covariate. An unstructured variance-covariance matrix will be fitted to model the dependency between repeated observations. Graphical checks on the model assumptions of normality of the data will be provided.

The mean treatment effects will be estimated at week 24. Together with the estimated covariance matrix, they will be used in the dose-response modeling as described below.

[figure not shown]
To allow adjustment for correlations between time points within patients, this MMRM approach is adopted to obtain the least squares means (LSM) fits.

The mean responses at each individual dose will be obtained through covariate-adjusted treatment effects by modeling the primary efficacy variable using a mixed-effect model for repeated measures (MMRM). The model will contain terms (factors) given above. Treatment group, visit, and geographical region will be fitted as categorical variables and baseline score as a continuous covariate. The model will be fitted using the SAS procedure “PROC MIXED”. Unstructured covariance matrix will be used (TYPE = UN), thus allowing adjustment for correlations between time points within patients. In order to get the variance covariance matrix of treatment effects to be full rank matrix, no intercept option will be used (NOINT option in MODEL statement). Adjusted means and the corresponding variance covariance matrix will be estimated. The estimated treatment differences for all treatment comparisons will be tabulated along with the associated 90% confidence intervals (ALPHA = 0.1) and two-sided p-values. No adjustment for multiplicity will be made. The estimated treatment means along with 90% CIs will be presented graphically as well. For calculation of denominator degrees of freedom Kenwood-Rogers method would be used (DDFM=KR)

In case the MMRM model does not converge the following sequential steps will be used:

1. change ddfm=kr to ddfm=bw. If still no convergence, perform step 2.

2. change type=un to type=cs. If still no convergence, perform step 3.
3. remove covariates in the following order until convergence: geographic region, stratification factor, treatment group by visit interaction.

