9.4 Analysis of the primary variable(s)

The purpose of this study is to characterize the dose response relationship among VAY736 doses (5, 50, 300 mg s.c. every 4 weeks) and placebo with regards to the change from baseline in ESSDAI at week 24 using all ESSDAI data collected during the 24 weeks of treatment during period 2. The goals of the study are:

- to confirm an overall dose-response signal, and
- to estimate the optimum dose that corresponds to the clinically relevant effect (i.e., 3-point change in ESSDAI) over placebo.

The generalized MCP-Mod methodology ([Bretz et al., 2005](#); [Pinheiro et al., 2014](#)) will be used to address these goals. Testing will be done at one-sided 5% alpha level.

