9.5.1 Efficacy variables

The following variables will be analyzed using a similar MMRM model as in the primary analysis:

- Change from baseline in ESSPRI, FACIT-F, SF-36 (PCS and MCS), PhGA, PaGA and salivary flow rate (unstimulated and stimulated) over 24 weeks

The MMRM model is fitted to the respective variables changes from baseline including the time points specified above and will include the following explanatory variables:

- treatment group
- visit
- treatment group by visit interaction
- baseline value of variable analyzed,
- stratification factor baseline ESSDAI score <10 or \geq 10
- geographic region.

The estimated means per dose and visit will be derived together with the 2-sided 95% confidence intervals. No hypothesis testing will be done.

For all parameters, summary statistics and listings together with graphical presentations of the original values and the changes from baseline will be presented by visit..

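### The primary MMRM gives baseline ESSDAI one slope for all six visits; a baseline-by-visit term would protect week-24 precision at almost no cost

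*SAP*

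**What the plan says.** SAP 5.4.1.1 fits the model to change from baseline in ESSDAI "including all time points until week 24 including the following fixed factors": treatment group, visit, treatment by visit, the ESSDAI stratum (below 10, or 10 and above) and region. It then adds "as well as baseline ESSDAI as a continuous covariate". The list is closed: "The model will contain terms (factors) given above". Protocol 9.4.2.1 gives the same model. SAP Table 5-1 shows six post-baseline visits, weeks 4, 8, 12, 16, 20 and 24.

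The covariance is left free: "An unstructured variance-covariance matrix will be fitted to model the dependency between repeated observations". Of the week-24 means the SAP says: "Together with the estimated covariance matrix, they will be used in the dose-response modeling as described below". Protocol 9.4 sets the level for that step: "Testing will be done at one-sided 5% alpha level".

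The secondary MMRMs in protocol 9.5.1 have the same form, with "baseline value of variable analyzed" as a main effect.

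**The concern.** Treatment effects and covariance may differ at every visit, but the main prognostic covariate may not. The outcome is a change score, so its slope on baseline depends on how strongly each visit still correlates with baseline. If that correlation fades, the slope steepens with time. A single fitted slope is then a weighted average that can lie close to the early-visit value.

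Week 24 alone feeds the dose-response test. Any mismatch between the fitted slope and the week-24 slope goes into the week-24 residual variance, and so into the covariance matrix that MCP-Mod uses. At stake is some power and a wider interval around the dose-response curve.

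**Working it through.** **Inputs from the documents.** About 45 patients per arm in four arms; six post-baseline visits; the model terms above; one-sided 5% testing; a 3-point relevant effect (protocol 9.4). The visible text gives no SD, dropout rate, baseline correlation or power figure, so there is no planned figure to reproduce. Everything below on correlation and SD is assumed.

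**Formulae.** Slopes use the SAP's sign (week 24 minus baseline).
- Slope at visit t: b_t = (correlation with baseline) × (SD_t / SD_0) − 1.
- Common slope in large samples, complete data: b* = 1′Wb / 1′W1, where W is the inverse of Σ + v(b − b*)(b − b*)′, b is the vector of visit slopes, Σ the residual covariance and v the baseline variance.
- Week-24 variance ratio, common slope over by-visit slopes: 1 + v(b_24 − b*)² / σ²_24.

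**Worked case.** Equal SDs (v = 1), autoregressive correlation 0.9 per visit, 10% measurement error. The correlation with baseline is 0.9 × 0.9 = 0.81 at week 4 and 0.9 × 0.9⁶ = 0.478 at week 24. The slopes are −0.19 and −0.522, and the fitted common slope is −0.273. Then σ²_24 = 1 − 0.478² = 0.771, and the ratio is 1 + 0.249² / 0.771 = 1.08.

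**Other serially decaying structures.**

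| Assumed structure | Variance ratio |
|---|---|
| AR 0.95, 10–20% error | 1.02–1.04 |
| Random intercept + AR + error | about 1.03 |
| AR 0.8, 10% error | 1.11 |
| AR 0.9 or 0.8, no error | 1.15–1.18 |
| Compound symmetry (constant slope) | 1.00 |

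**A second grid.** Here the correlation runs linearly from week 4 to week 24, with baseline SD 5 and residual correlation AR(0.8) or CS(0.6). Power is for one dose against placebo, 45 per arm, as a stand-in for the MCP-Mod contrast.

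| Correlation, week 4 to 24 | SE ratio | Power, planned vs by-visit |
|---|---|---|
| 0.7 to 0.7 | 1.000 | 99.0% vs 99.0% |
| 0.7 to 0.6 | 1.003 | 97.1–97.2% vs 97.2% |
| 0.8 to 0.5 | 1.033–1.050 | 93.1–93.8% vs 95.0% |
| 0.85 to 0.4 | 1.08–1.13 | 86.6–88.8% vs 92.8% |
| 0.9 to 0.3 (extreme) | 1.17–1.24 | 78–82% vs 91% |

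If the correlation instead rises from 0.6 to 0.7, or the ESSDAI SD grows by 20% at constant correlation, week 24 is over-adjusted, at an SE cost of 0.1–0.7%.

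**Simulation with stratum and region in the model.** 180 patients, four arms, allocation balanced within strata, 0% or 15% dropout unrelated to outcome, 200–250 runs per case. Model-based SE ratios were 1.000–1.001 (constant slope), 1.003 (0.7 to 0.6), 1.032–1.054 (0.8 to 0.5) and 1.173 (0.9 to 0.3). Empirical SE ratios in the varying-slope cases were 1.01–1.08, which is noisy at 200 runs. Mean week-24 differences were −2.99 to −3.09 under both models, against a true −3.

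**Model-based against sampling variance.** 500 runs, stratified allocation, stratum in the model, complete data, residual AR(0.8).

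| Residual SD | Slope, week 4 to 24 | Model variance ratio | Sampling variance ratio |
|---|---|---|---|
| 2.5 rising to 4 | −0.1 to −0.5 | 1.07 | 1.03 |
| 2.5 rising to 4 | −0.1 to −0.7 | 1.17 | 1.07 |
| 3.75 constant | −0.1 to −0.5 | 1.03 | 1.02 |
| 3.75 constant | −0.1 to −0.7 | 1.07 | 1.04 |

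**Dropout that is missing at random but informative.** 40,000 simulated patients, two arms, true difference −3, 17–18% dropout depending on baseline or last observed value in opposite directions by arm; stratum and region omitted. The common slope gave −3.20 to −3.31 and by-visit slopes gave −2.99 to −3.05 (SE about 0.05). The common-slope error is 0.20–0.31 points, or 7–10% of 3. The pattern was deliberately strong.

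**The case against.** The strongest reply is that the loss is hypothetical. Nothing visible shows that the slope varies. If it is constant nothing is lost, and a mild fall in correlation costs 0.3% of the SE. That stands: a reader might infer that the week-24 means are under-adjusted as a matter of fact, and the documents do not support this. The direction can even reverse.

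Second, chance baseline imbalance is already limited by design. The "stratification factor baseline ESSDAI score" enters both randomization and model. With an assumed baseline SD of 3.4, unstratified allocation would give a pairwise imbalance SD of 3.4 × √(2/45) = 0.72. Blocked allocation within the strata, with an assumed 37% at or above 10, gave 0.44–0.47 in simulation. So the estimates vary less than the model-based SE suggests. This also stands, but MCP-Mod uses the model-based covariance, so a power cost can remain.

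Third, a reader might infer that the planned test is biased or invalid. It is not, on this evidence: estimates were unbiased when dropout was unrelated to outcome, and in the decaying-correlation cases the restriction widens the SE. Bias needed dropout tied to baseline or observed outcome and differing by arm.

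Fourth, protocol 9.5.1 plans no hypothesis tests on the secondary variables, SAP 2.6.2 is largely redacted, and no secondary endpoint was simulated. The case for changing those models is therefore consistency only.

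None of this identifies a disadvantage of the extra term.

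**Conclusion.** The point holds in conditional form. The plan fits one baseline slope to six visits and uses only week 24 in the dose-response step. If the slope varies by visit, week 24 is mis-adjusted. Its model-based variance is then roughly 2–18% larger than necessary under the serially decaying correlations assumed here. A mild linear fall (0.7 to 0.6) gives about 0.5%; steep falls (to 0.4 or below at week 24) can exceed 18%. The excess in sampling variance is smaller, and there is none if the slope is constant.

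The size cannot be fixed from the documents. The issue is mainly efficiency, with bias only under the dropout pattern described. The change is worth making because the payoff is one-sided: with constant slopes the SE ratio was 1.000–1.001, so the extra term cost essentially nothing.

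**What to change.** - Add a baseline ESSDAI-by-visit interaction to the primary MMRM in SAP 5.4.1.1 and protocol 9.4.2.1, before unblinding so that it cannot look data-driven.
- For consistency, add baseline value by visit to the secondary MMRMs in protocol 9.5.1 and the matching SAP text.
- In the non-convergence sequences of SAP 5.4.1.1 and 5.4.2, name this interaction as the first fixed effect removed, ahead of region, stratum and treatment by visit.
- Consider stratum by visit too, since the stratum is a second baseline-severity term with one effect across visits.

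The primary change costs five degrees of freedom, against at most 180 × 6 = 1,080 observations, and needs no new data. Stratum by visit would cost another five.
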